## 1 Background / Scientific Rationale

In the United States it is estimated that 47 million people have been diagnosed with arthritis. 4.3 million have been diagnosed with isolated osteoarthritis of the knee and knee arthritis accounts for 20% of disability claims [1]. Prevalence of the disease continues to climb and is expected to double by 2030. In addition, 4 out of 5 patients with osteoarthritis have movement limitations [1]. Currently there are no curative treatments for osteoarthritis. Surgical options include arthroscopy, osteotomies, and total joint replacement, but not all patients with knee osteoarthritis are candidates for surgical treatments, and others choose non-operative treatments instead of undergoing a procedure. Non-surgical treatment options include medications such as non-steroidal anti-inflammatory's (NSAIDs), injectables such as corticosteroids and hyaluronic acid, or physical treatments such as rehabilitative therapy, unloading braces, and activity modifications (i.e. canes or walkers). Additionally, weight loss can help in the battle to reduce pain in cases of knee osteoarthritis.

The clinical efficacy of hyaluronic acid or corticosteroid injections has been reported, but effects are short lived. This has led to the development of additional injection options such as autologous derived blood products which have been documented to alleviate symptoms related to knee osteoarthritis, with recent comparative studies suggesting a greater, long-lasting effect with these blood derived products like platelet rich plasma (PRP) [2-8]. One clinically-developed preparation of platelet rich plasma, named autologous conditioned plasma (ACP), has randomized controlled trial data proving efficacy [4,9]. Clinical use of platelet rich plasma for knee arthritis typically involves a 3-injection series over 3 weeks, i.e. an injection once a week for three weeks. Currently, all three orthopedic providers in this study use ACP to treat patients with knee osteoarthritis in common accepted clinical practice.

# 2 **Objectives**

The main objective of this study is to determine if hyaluronic acid (HA) injected at the same time as autologous conditioned plasma (ACP), a leukocyte-poor platelet rich plasma product, will improve the performance of ACP in the treatment of symptomatic knee osteoarthritis. We hypothesize that the injection of hyaluronic acid will improve the efficacy of ACP.

## **3** Participant Eligibility

*Inclusion Criteria*: Patients between the ages of 30 and 80 who have documented radiographic evidence of OA in the tibiofemoral or patellofemoral compartment of the target knee (Kellgren-Lawrence grades 1-4) will be screened for participation in this study. Patients must have a documented diagnosis of primary OA for at least 6 weeks.

```
Version 3.0
6/19/2019
```

#### A Randomized, Control Clinical Trial: The Effect of Different Injection Regimens of Autologous Conditioned Plasma for the Treatment of Symptomatic Knee Osteoarthritis [name]. Page 4 of 7

*Exclusion criteria*: Patients who have had viscosupplementation in the involved knee in the past 6 months. Any patient who has had a corticosteroid injection in any joint within 3-months prior to screening will be excluded. Patients with gout or rheumatologic disease will be excluded. Patients who have had a previous negative experience with HA. Any patient who will have difficulty obtaining internet access, does not have an active e-mail address, or is unable to comprehend study documents or give informed consent will be excluded.

# 4 Participant Enrollment

80 patients will be recruited through the Andrews Institute physician practices. Potential participants will be prescreened for inclusion and exclusion criteria through standard of care medical evaluations. Once a potential participant has agreed to be involved in the study, they will go through the described informed consent process. Patients meeting the inclusion criteria will have the study explained to them by one of the members of the investigating team, and they will be given an opportunity to participate if they are interested. No specific advertising or recruitment material will be utilized.

Participant will also be instructed that they must not take any prescription or over the counter non-steroidal anti-inflammatory drugs (NSAIDS) for 1 week prior to the first injection until after the final injection. The participants will then be randomly placed in one of the two study groups and be scheduled to receive a three-injection series of autologous conditioned plasma injection or a two-injection series of autologous conditioned plasma and hyaluronic acid and a third injection on the third week of ACP in their involved knee. For The group receiving autologous conditioned plasma and hyaluronic acid, HA will be an additional injection on the first two injections and the third injection will be ACP alone. This regimen was selected to reflect the current evidence-based regimens for ACP and HA independently.

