## 5 Study Design and Procedures

Study design will be randomized control trial. Participants who meet the inclusion criteria will have the study explained in detail and informed consent will be obtained as outlined above. Participants will complete patient reported outcome questionnaires prior to their injection. The questionnaires will include the Western Ontario and McMaster University's Osteoarthritis Index (WOMAC), International Knee Documentation Committee Subjective Knee Evaluation Form (IKDC), Knee Injury and Osteoarthritis Outcome Score (KOOS). The WOMAC is 24 questions and takes approximately 2-5 minutes, the IKDC is 19 questions and takes 3-5 minutes, and the KOOS is 42 items and takes approximately 5-10 minutes. Participants will also complete these questionnaires at 1, 3, 6, 12, 18, and 24 months after the final injection.

Version 3.0 6/19/2019

#### A Randomized, Control Clinical Trial: The Effect of Different Injection Regimens of Autologous Conditioned Plasma for the Treatment of Symptomatic Knee Osteoarthritis [name]. Page 5 of 7

A trained medical professional will draw blood from the patients arm and the blood will be spun in a centrifuge for 5 minutes at 1500 RPM. The platelets will then be separated off for injection into the patient's knee. The treating physician will then inject the ACP into the involved knee joint following standard aseptic technique per the physician's standard of care. This entire process will be completed in a single patient visit. Any unused portion of a sample in the physician's office will be disposed of through standard biohazard waste disposal systems as required by law.

Group 1 [ACP]: Will receive 3 intra-articular injections of autologous conditioned plasma dosed at once a week for 3 weeks. Group 2 [ACP-HA]: Will receive 2 intra-articular injections of autologous conditioned plasma and hyaluronic acid once a week for 2 weeks and a third injection on the third week of ACP.

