# 11 Regulatory Requirements

## **Informed Consent:**

The informed consent process will be performed by one of the study investigators or staff, in the office. All participants will have the study described to them and will give as much time as they require to read an approved, stamped version of the informed consent document. After signing of the informed consent document, participants will be given a copy for their records. This process will take place only after the patient has consented to proceed with the study.

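### Random assignment comes at or before scheduling, leaving a gap of unstated length before the first injection in which losses and baseline answers could differ by arm

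*Combined protocol and SAP*

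**What the plan says.** Section 4 sets out the steps in order. Patients are prescreened, a team member explains the study (the patient "will have the study explained to them by one of the members of the investigating team"), and consent follows. Section 11 adds: "The informed consent process will be performed by one of the study investigators or staff, in the office". Participants are then told to avoid "non-steroidal anti-inflammatory drugs (NSAIDS) for 1 week prior to the first injection until after the final injection". After that comes the assignment: "The participants will then be randomly placed in one of the two study groups and be scheduled to receive a three-injection series", or the series with HA added.

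The arms differ visibly in treatment. In the combination arm, "HA will be an additional injection on the first two injections and the third injection will be ACP alone". Both arms attend once a week for three weeks (Section 5).

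Section 5 places the baseline WOMAC, IKDC and KOOS before the injection, without saying whether they come before assignment. Beyond the steps in Section 4, the only design statement is "Study design will be randomized control trial". The text gives no sequence method, allocation ratio, list holder, concealment, blinding or sham. Section 9 defines no analysis population and does not say how a patient who is randomised but never injected is counted.

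**The concern.** Randomisation makes the arms comparable at the moment of assignment. Any interval between that moment and first treatment lets patients drop away, and if the assignment is known the dropping away can depend on it. A patient who leaves before the questionnaires and the first injection contributes no data, so the repeated measures ANOVA in Section 9 cannot recover that patient.

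The same interval affects the baseline. All three instruments are self-reported. If they are completed after the patient knows the arm, the baseline scores may already reflect expectation. Section 2 hypothesises that adding HA improves the result, so expectation need not be equal in the two arms.

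What is at stake is bias in the between-arm comparison. This is separate from the adequacy of the sample size.

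**Working it through.** **1. Order of steps.**
- Section 4 gives the NSAID instruction, then random placement, then (or together with it) scheduling.
- The NSAID-free period is dated backwards from the first injection: "must not take any prescription or over the counter non-steroidal anti-inflammatory drugs (NSAIDS) for 1 week prior to the first injection".
- The injection date is fixed at scheduling, which is at or after assignment. The NSAID-free week therefore most naturally falls after assignment. This is an inference; the protocol does not state it or give the interval.
- Section 5 requires the questionnaires only before the injection, so they may fall on either side of assignment.

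**2. The plan's own figure.** Section 9 gives 25 per group at 80% power and p < 0.05. It states no effect size, SD or sidedness, so the figure can be neither reproduced nor refuted. Solving for the standardised effect it implies:
- Two-sided, normal approximation: (1.960 + 0.842) × √(2/25) = 0.79 SD (0.81 with the t distribution).
- One-sided: 0.70 SD.

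Section 4 recruits 80 against the 2 × 25 = 50 required. Since 50/(1 − 0.375) = 80, a loss of 37.5% would still leave 50.

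**3. Effect on power.** Assume 40 per arm (1:1 is not stated), a two-sided 5% test, 80% power and the noncentral t distribution.
- 40 v 40: detectable difference 0.634 SD.
- 40 v 36 (4 of 40 lost from one arm): 0.652 SD.

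The change is 0.018 SD, which is negligible.

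**4. Effect on bias.** Let f be the share lost from one arm and D the difference between stayers and leavers in mean outcome. The full-arm mean is (1 − f) × stayers + f × leavers, so the stayers' mean departs from it by f × D. With D = 0.5 SD (assumed):
- 4 of 40: 0.10 × 0.5 = 0.05 SD.
- 8 of 40: 0.20 × 0.5 = 0.10 SD.

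**5. A harsher illustration.** Suppose the fraction f with the worst baseline leaves one arm, there is no true effect, and the test is unadjusted. With baseline-outcome correlation ρ, the bias is ρ × φ(z_f)/(1 − f), where φ is the standard normal density and z_f its f-quantile. The standard error is √(1/40 + 1/(40(1 − f))). At ρ = 0.5:

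| f | Bias (SD) | Standard error (SD) | False-positive rate |
|---|---|---|---|
| 5% | 0.5 × 0.103/0.95 = 0.05 | 0.227 | 5.7% |
| 10% | 0.5 × 0.175/0.90 = 0.10 | 0.230 | 7.1% |
| 20% | 0.5 × 0.280/0.80 = 0.18 | 0.237 | 11.4% |

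For ρ from 0.3 to 0.7, the 20% case runs from 7.3% to 17.8%. This is a severe pattern: all losses come from one arm and all are the worst-baseline patients. Every f, D and ρ here is an assumption.

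**The case against.** The strongest reply is that much of this depends on what the protocol leaves unsaid. Several stronger readings are tempting, and the text does not support them.

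- **That the allocation list is open, so entry depends on the arm.** The protocol is silent on concealment; it does not say the next assignment is visible. Consent and eligibility come before assignment in Section 4, so only a foreseeable sequence could influence entry. The exclusion for "Patients who have had a previous negative experience with HA" has no definition and would leave room for discretion in that case, but nothing shows the sequence is foreseeable.
- **That the booking reveals the arm.** Section 4 describes scheduling by regimen, but not who sees it, and both arms share the same weekly visits.
- **That patients are told their arm before treatment.** No section says so. The extra injection would probably reveal it at treatment, which is later than this argument needs.
- **That patients who cannot stay off NSAIDs leave after randomisation.** Section 4 gives an instruction. It does not make NSAID use a ground for withdrawal or for withholding the injection.

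It is also fair to say that the size is modest and assumed, that the extra recruitment absorbs the power loss, and that moving randomisation does nothing for losses between injections or over the 24 months of follow-up. Undescribed concealment would, alone, be a missing detail.

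What remains is a stated step. Assignment comes at or before scheduling, the baseline is tied only to the injection, and no safeguard is described for the interval between.

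**Conclusion.** The point holds in a limited form. As written, there is a gap of unstated length between assignment and first treatment, probably including the NSAID-free week, in which losses and baseline self-reports could differ by arm. The documents do not show that this happens.

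The illustrative bias is 0.05 to 0.10 SD for a 10% to 20% loss from one arm. It rests on an assumed 0.5 SD difference between leavers and stayers, and the documents supply no loss rate. If the losses were exactly the worst-baseline patients, at an assumed correlation of 0.5, the same loss rates would give about 0.10 to 0.18 SD. The sample size need not change. The amendment is worth making because it is cheap and because a selective loss cannot be undone afterwards.

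**What to change.** Revise Section 4, with matching wording in Section 5:

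1. Book every patient for the same three weekly visits before assignment. Both arms already follow this pattern.
2. Randomise at the first-injection visit, after consent, the existing Section 3 eligibility check and completed baseline questionnaires.
3. Release the assignment only then, from a list concealed from those who recruit. A REDCap randomisation module would serve if available (Section 8 names REDCap for data entry only), as would sequentially numbered sealed opaque envelopes.
4. State in Section 9 that any losses between randomisation and first injection will be reported by arm.

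Do not make NSAID abstention a condition of randomisation. That would add an entry rule absent from Section 3. The existing instruction stays unchanged.

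Cost: a few sentences of protocol text, HA available at every first visit, a first visit whose length is not known beforehand, and someone not involved in recruiting to prepare the list.

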## 5 Study Design and Procedures

Study design will be randomized control trial. Participants who meet the inclusion criteria will have the study explained in detail and informed consent will be obtained as outlined above. Participants will complete patient reported outcome questionnaires prior to their injection. The questionnaires will include the Western Ontario and McMaster University's Osteoarthritis Index (WOMAC), International Knee Documentation Committee Subjective Knee Evaluation Form (IKDC), Knee Injury and Osteoarthritis Outcome Score (KOOS). The WOMAC is 24 questions and takes approximately 2-5 minutes, the IKDC is 19 questions and takes 3-5 minutes, and the KOOS is 42 items and takes approximately 5-10 minutes. Participants will also complete these questionnaires at 1, 3, 6, 12, 18, and 24 months after the final injection.

Version 3.0 6/19/2019

#### A Randomized, Control Clinical Trial: The Effect of Different Injection Regimens of Autologous Conditioned Plasma for the Treatment of Symptomatic Knee Osteoarthritis [name]. Page 5 of 7

A trained medical professional will draw blood from the patients arm and the blood will be spun in a centrifuge for 5 minutes at 1500 RPM. The platelets will then be separated off for injection into the patient's knee. The treating physician will then inject the ACP into the involved knee joint following standard aseptic technique per the physician's standard of care. This entire process will be completed in a single patient visit. Any unused portion of a sample in the physician's office will be disposed of through standard biohazard waste disposal systems as required by law.

Group 1 [ACP]: Will receive 3 intra-articular injections of autologous conditioned plasma dosed at once a week for 3 weeks. Group 2 [ACP-HA]: Will receive 2 intra-articular injections of autologous conditioned plasma and hyaluronic acid once a week for 2 weeks and a third injection on the third week of ACP.

### 6 Expected Risks and Benefits

**Risks and Discomforts:** Potential risks include those expected with any injection including syncope, dizziness, headache, nausea, tachycardia, infection (septic arthritis, phlebitis, and osteomyelitis), bleeding, or pain. Additionally, participants may experience knee stiffness or inflammation associated with the procedures. These risks would not be any higher with the test interventions than those patients are subject to with injection treatments of knee OA. As with any research involving patients there is the inherent risk of a breach in patient confidentiality though this will be minimized through the use of participant code numbers and adherence to all HIPAA guidelines.

Benefits: Direct benefits of the study include injections that may provide potential pain relief, improvement of knee function, and improvement of quality of life, which all could lead to the avoidance of surgical intervention. It is also believed that the information obtained in this study will help advance treatment of osteoarthritis through the use of regenerative medicine.

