# 9 Statistical Considerations

A power analysis was performed to determine sample size based upon recent clinical trials comparing PRP to HA for the treatment of osteoarthritis. Analysis utilized the average of standard deviation to detect average of group mean effect at 80% power. This determined that 25 patients per group would be needed to reach statistical significance with the WOMAC.

Ranges, means and standard deviations for all measures will be determined and calculated. Data will be analyzed for differences between groups using a repeated measures ANOVA design, using a significant p-value of < 0.05 for rejecting the null hypothesis.

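### No section records or analyses adverse events although one arm receives an added product, so the Section 6 risk statement is unsupported and untested

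*Combined protocol and SAP*

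**What the plan says.** Section 6 gives the expected harms: "Potential risks include those expected with any injection including syncope, dizziness, headache, nausea, tachycardia, infection (septic arthritis, phlebitis, and osteomyelitis), bleeding, or pain". It adds knee stiffness and inflammation, then concludes: "These risks would not be any higher with the test interventions than those patients are subject to with injection treatments of knee OA". No source is cited and the two arms are not discussed separately.

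The arms are described in two places. Section 4 says of the combination group that "HA will be an additional injection on the first two injections and the third injection will be ACP alone". Section 5 says that Group 1 "Will receive 3 intra-articular injections of autologous conditioned plasma dosed at once a week for 3 weeks", and that Group 2 "Will receive 2 intra-articular injections of autologous conditioned plasma and hyaluronic acid once a week for 2 weeks", followed by ACP in the third week.

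For data collection, Section 5 says: "Participants will complete patient reported outcome questionnaires prior to their injection". The questionnaires are WOMAC, IKDC and KOOS, repeated at 1, 3, 6, 12, 18 and 24 months after the last injection. Sections 7 and 8 deal with storage and databases. Section 9 plans a repeated measures ANOVA and says: "Ranges, means and standard deviations for all measures will be determined and calculated". Section 10 provides for accuracy checks, and Section 11 covers consent and confidentiality.

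**The concern.** The objective in Section 2 is to learn whether adding HA improves ACP. A favourable answer would support giving patients a second product, and that decision needs harms set beside benefit. Followed as written, the trial would have no systematic harms data from either arm. Acute events that nobody asks about at the time cannot be reliably reconstructed at 24 months.

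The risk sentence makes this sharper. It reassures about the test interventions, yet nothing in the plan supports it and nothing in the plan could test it. Section 4 says the regimen reflects evidence for ACP and HA taken independently, so it offers no evidence on the two together. Section 3 excludes patients with a bad prior experience of HA, but Section 6 names no risk specific to HA.

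**Working it through.** **1. Is any harm captured?** The plan contains no safety figure to reproduce; the 25 per group in Section 9 concerns WOMAC only. Setting the Section 6 list against what is collected:

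- Syncope, dizziness, headache, nausea, tachycardia, infection and bleeding: no form or field is described for any of them.
- Pain, stiffness and inflammation: WOMAC and KOOS may reflect pain or stiffness that persists, but as outcome scores, without onset date, seriousness or attribution.
- Timing: three weekly injections span 2 weeks, so the 1-month form falls about 2 + 4 = 6 weeks after the first injection. A reaction between weekly visits would usually have passed by then.
- Analysis: Section 9 has no safety summary, and Section 10 has no event review or reporting.

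**2. How many injections per arm?** Group 1 has 3 (Section 5).

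- If HA is a separate injection at the first two visits (Section 4 read literally), Group 2 has 3 + 2 = 5, and 5/3 = 1.67, or 67% more.
- If Section 5 means combined injections, Group 2 has 2 + 1 = 3. The arms then differ only in the added product.

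The added product is common to both readings.

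**3. Illustration of scale.** The inputs here are assumptions, not figures from the documents: a per-injection risk p, independence between injections, and HA given separately. The chance of at least one event in a patient is 1 − (1 − p)^k, with k = 3 or 5.

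| p | 3 injections | 5 injections |
|---|---|---|
| 1% | 3.0% | 4.9% |
| 5% | 14.3% | 22.6% |
| 10% | 27.1% | 41.0% |

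Under the three-injection reading this difference is zero. The documents give nothing from which to size an effect of the product itself.

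**4. What could the trial show if events were recorded?** Section 4 plans 80 patients. The allocation ratio is not stated, so 40 per arm assumes 1:1.

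- Zero events in n patients, one-sided 95% upper limit 1 − 0.05^(1/n): 7.2% for n = 40, and 11.3% for n = 25. This bounds the absolute risk in one arm and does not compare arms.
- Risk difference, 5% row: 22.6 − 14.3 = 8.4 points before rounding. Standard error √[(0.1426×0.8574 + 0.2262×0.7738)/40] = 0.086. The 95% interval is 8.4 ± 16.9, about −8.5 to 25.3 points.
- Risk difference, 10% row: 13.9 points, standard error √[(0.271×0.729 + 0.4095×0.5905)/40] = 0.105. The 95% interval is 13.9 ± 20.5, about −6.7 to 34.4 points.
- Power at 40 per arm (two-sided 5%, normal approximation): about 16% for the 5% row and 25% for the 10% row.

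Recording events would therefore give a useful description, but not proof of equal or lower risk.

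**The case against.** A reader might infer that the design contradicts the risk sentence, since Group 2 gets everything Group 1 gets plus HA. The documents do not support that. The sentence compares the test interventions with knee OA injection treatments as a class, not one arm with the other. Section 1 names corticosteroid and HA injections within that class as well as platelet rich plasma. The sentence lacks support, but it makes no between-arm claim for the design to refute.

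A reader might also take two extra injections as settled. That count rests on one sentence in Section 4, and Section 5 can be read as three injections. Section 2 says only that HA and ACP are given at the same time, which fits either reading.

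The percentages are open to challenge too. The per-injection risks are not from the documents, and independence is doubtful for two products put into the same knee at one visit. They show scale and are not evidence of harm.

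Finally, it is too strong to say that the plan would see nothing at all, because WOMAC and KOOS may pick up lasting pain or stiffness. These objections narrow the point. They leave its core standing: no numbered section describes recording, reporting or analysing adverse events. The consent pages were not available for this review, but data collection and analysis belong in the numbered sections, which are present.

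**Conclusion.** The point holds in this form. The protocol adds a product to one arm and has no adverse event collection, reporting or analysis in either arm. The Section 6 sentence is therefore unsupported and untested, though not contradicted. Listed harms such as syncope, infection and bleeding would go unrecorded, and this affects what the trial does, not only how it is described. It leaves the WOMAC, IKDC and KOOS comparison unaffected, but that comparison would have to be interpreted with no harms beside it.

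The size of any difference in risk cannot be derived from the documents. The figure of 67% more injections is conditional on HA being given separately. The 7.2% limit and the interval widths assume 1:1 allocation with 40 per arm. The finding that no events are collected depends on none of these assumptions.

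**What to change.** - **Section 5:** add a short adverse event form at the second and third injection visits and with the 1-month questionnaires, the same in both arms. It should hold one open-ended question plus the events listed in Section 6, with date and seriousness. The open question matters because the Section 6 list is generic to injections and could miss events specific to the added product.
- **Section 9:** report, descriptively, the number of participants in each arm with at least one event, with a risk difference and 95% interval. State that about 40 per arm (assuming 1:1) gives low precision and cannot establish that risk is no higher.
- **Section 6:** replace the sentence on risks with a statement that Group 2 receives HA in addition to ACP and that adverse events will be recorded in both arms. Match the consent wording.
- **Sections 4 and 5:** reconcile whether HA is a separate injection, so that injections per arm can be counted.

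The cost is one brief form at contacts that already take place, one table and a text edit. The downside is a little staff and patient time. Treatment, visit schedule and sample size are unchanged.
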